2.5. Study Design

This study will employ a randomized, double-blind, active placebo-controlled design. Twelve patients with treatment-resistant PTSD will be randomly assigned after baseline assessment to either 3 MDMA-assisted sessions with a full dose of 125mg MDMA followed by a supplemental dose of 62.5mg MDMA administered 2.5 h later, or to an active placebo dose of 25mg MDMA followed by 12.5mg MDMA 2.5h later. Participants will undergo three sessions of MDMA-assisted psychotherapy scheduled to occur three to five weeks apart, 1 non-drug-psychotherapy session 24 h after each MDMA-session and 2-4 weekly, integrative psychotherapy sessions after each MDMA session. PTSD symptoms will be assessed by an independent assessor once prior to MDMA-assisted psychotherapy, 3 weeks after the second MDMA-assisted session, 3 weeks after the third experimental session, marking the end of non-drug psychotherapy, and two, six and twelve months later, with the CAPS serving as a primary outcome measure. Participants assigned to the active placebo condition will be given the opportunity to take part in an open-label continuation of the study, referred to here as “Stage 2.” Data gathered 3 weeks after the third experimental session will be treated as the baseline for Stage 2, and outcome measures will be administered 3 weeks after the second and third experimental session, 2, 6, and 12 months after baseline for all patients who consent to take part in Stage 2. Participants receiving the full dose in either Stage 1 or Stage 2 and not responding with significant improvement will be offered the opportunity to take part in an open-label continuation of the study, referred to as “Stage 3”, consisting of 2 additional MDMA sessions. During these sessions, they may receive 125 mg followed 2.5 hours later by 62.5 mg MDMA, or a 20% larger dose of 150 mg MDMA, followed by a supplemental dose of 75 mg administered 2.5 hours later. Outcome measurements gathered at 2 months after the third experimental session will serve as baseline measures for Stage 3. Procedures for non-drug psychotherapy sessions, experimental sessions and outcome measure administration will be the same as those employed in the first stage of the study.

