2.7. Participants

The first twelve participants who meet all inclusion criteria without meeting any exclusion criteria will be admitted to the study. Participants enrolled in the study who withdraw during treatment or who the researchers decide for any reason should not continue in the study (“drop-outs”) will be replaced. Participants will be recruited for the study by call for referral from specialized institutions such as trauma advice and counseling centers (outpatient clinics for psychotraumatology), as well as psychiatrists and psychotherapists in private practice (see enclosed).

2.7.1. *Inclusion Criteria*

Participants who meet the following criteria will be considered for inclusion in this study:

1. Participants must meet DSM IV criteria for current PTSD (within the past 6 months) in response to a traumatic experience. An individual would not be excluded if she or he experienced more than one traumatic event. Participants must have a CAPS score of 50 or higher, indicating moderate to severe PTSD symptoms.
2. They must have had at least one unsuccessful attempt at treatment for PTSD. Treatments include psychotherapy and pharmacotherapy. Pharmacotherapies may include selective serotonin uptake inhibitors (SSRIs). Psychotherapeutic treatments may include, but are not limited to cognitive-behavioral therapy (including exposure therapy), stress inoculation training, including anxiety management, and insight-oriented psychotherapy (Foa et al. 2003; Jaycox et al. 2002; Krupnik 2002; Resick and Schnicke 1992). Treatment will be deemed unsuccessful if the participant continues to meet criteria for current PTSD following the treatment.
3. Participants may also meet criteria for a mood disorder (except bipolar affective disorder, see exclusions) and for other anxiety disorders. The inclusion of people with other mood and anxiety disorders is essential because recent literature (Brady et al., 1994; Faustman & White, 1989) indicates the marked frequency of the co-existence of other psychiatric disorders among patients with PTSD.
4. Participants must be at least 18 years old.
5. Participants must be willing to commit to medication dosing, therapy sessions, and follow-up sessions and to complete evaluation instruments.

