2.8.2. Assessments and Measures

Psychiatric diagnoses will be made through the Structured Clinical Interview for Diagnoses (SCID), and PTSD symptoms will be measured by the Clinician Administered PTSD Scale (CAPS) during screening to determine whether an individual may participate in the study.

PTSD symptoms will be assessed six times in this study:

- T0: *Baseline assessment*
- T1: *Post MDMA 2 assessment*: 3 weeks after the second experimental session (MDMA 2)
- T2: *End of treatment assessment*: 3 weeks after the third experimental session (MDMA 3)
- T3: *1st follow-up assessment*: 2 months after the third experimental session (MDMA 3)

T4: *2nd follow-up assessment*: 6 months after the third experimental session (MDMA 3) for all participants assigned to the Fully Active Dose condition, and all participants assigned to the Low Dose condition who choose not to take part in the open-label study continuation.

T5: *3rd follow-up assessment*: 12 months after the third experimental session (MDMA 3) for all participants assigned to the Fully Active Dose condition, and all participants assigned to the Low Dose condition who choose not to take part in the open-label study continuation.

Participants who choose to take part in the open label study continuation “Stage 2” will be assessed identically to stage 1 three weeks after the second and third (end of treatment) experimental sessions and two, six and twelve months after the third experimental session in Stage 2. The T2 assessment will serve as baseline for stage 2.

Participants who choose to take part in the open label study continuation “Stage 3” will be assessed identically to stage 1 three weeks after the second (end of treatment) experimental session and two, six and twelve months after the experimental session in Stage 2. The T3 assessment will serve as baseline for stage 3.

All outcome measures will be administered by an independent assessor. The independent assessor will remain blind to subject condition and will not be present during psychotherapy sessions. The CAPS will serve as the primary outcome measure, and the PDS will serve as additional measure of PTSD symptoms. The CAPS and the PDS are specifically designed to assess PTSD. German versions of all measures will be used in this study.

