Statistical significance will be set at 0.05. Because the sample size is very small, the study has sufficient power only to detect large effects. Therefore, there will be no adjustment for multiple testing; p-values and confidence intervals will be reported instead. We will assess participant CAPS and PDS scores at baseline and two months after each participant has undergone a final session, defined as the last experimental or open-label MDMA-assisted psychotherapy session, using the same nonparametric tests employed in comparisons of active placebo and experimental dose MDMA described above.

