17, 2003). Likewise, psychiatrists in the US and Europe reported using MDMA in a large number of patients before the drug was placed into Schedule I. When describing their experiences (Adamson 1985; Gasser 1994; Greer and Tolbert 1986; Greer and Tolbert 1998; Metzner and Adamson 2001; Stolaroff 2004; Widmer 1998), these therapists did not report any severe adverse effects occurring during or after MDMA-assisted psychotherapy sessions

In spite of this reassuring data, we intend to closely monitor closely for the unlikely possibility of an untoward reaction. The sessions will be conducted in a general medical setting where basic emergency equipment will be immediately available. [name] office is located five minutes from the next hospital, the Bürgerspital Solothurn, which has an emergency room and an intensive care unit. The hospital will be informed in advance about the nature of this study.

Hypertension and related cardiovascular complications:

Blood pressure and pulse will be measured at regular intervals (see table 3). If at any time the blood pressure exceeds 160 systolic or 110 diastolic, or the pulse exceeds 110, measurements will be taken every 5 minutes until the values fall below these levels or until they have been decreasing for 15 minutes or have stabilized at a level judged by the investigator to be safe. During this time the principal investigator will continually evaluate the patient for increasing blood pressure and signs or symptoms of a developing hypertensive or other cardiovascular emergency. The principal investigator will make a clinical judgment about whether additional monitoring or treatment is required. Reasons for moving a patient to an ICU would include, but not be limited to, severe headache in the setting of hypertension, angina or neurological deficits regardless of blood pressure. This will allow treatment to be instituted without transferring the participant if that should become necessary. The investigator may, at any time, make a clinical judgment to transfer the participant to the ICU for closer monitoring and additional treatment. Any participant who experiences sustained blood pressure of > 220 systolic or > 120 diastolic or heart rate > 75% predicted maximum during an experimental session will not be given a subsequent experimental session.

Angina or Myocardial Infarction:

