Participants hospitalized after a severe panic reaction will be suspended from study participation until after recovery or stabilization, at which time the investigator will carefully evaluate the participant's emotional status. If this response occurs during the first experimental session, the investigator may elect to forego the further experimental sessions and drop the participant from the study. This decision will be made after discussion with the ethics committee and any other appropriate regulatory agencies. For those participants engaged in an on-going therapeutic relationship, we will actively involve their outside therapists in the management of any psychiatric complications of treatment.

In the event of a participant's experiencing severe, persisting emotional distress, such as panic attacks, severe generalized anxiety or insomnia following an experimental session, the investigator may prescribe a benzodiazepine or zolpidem as a “rescue medication.” If a participant should become psychotic or suicidal, arrangements will be made for him or her to be admitted to the nearest inpatient psychiatric facility of their choice. Residual symptoms will be addressed during the frequent follow-up psychotherapy visits with the investigators.

Any participant who develops mania or psychosis will not be given a further MDMA session and will receive appropriate psychiatric treatment.

Hyperthermia:

If temperature rises more than 1° C, attempts will be made to lower it by removing blankets and layers of clothing, decreasing the ambient temperature and, if necessary, directing a fan toward the participant. If at any time the temperature rises more than 1.5° C above baseline despite these efforts, ice packs will be used, blood will be drawn for stat CBC, electrolytes, BUN, creatinine, glucose, CPK, PT, PTT, platelets and liver enzymes, and urine will be collected for urinalysis. If there are significant abnormalities in these tests, if the temperature continues to rise, or if an elevated temperature is associated with delirium or muscle rigidity the participant will be transferred to the nearest ICU. If, during the first or second experimental session, a participant's temperature rises more than 1 ° C. and does not rapidly come down after the above adjustments have been made in blankets, clothing, ambient temperature and ventilation, then that participant will not be given any subsequent experimental sessions.

Dehydration:

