In order to avoid dehydration, participants will be encouraged to drink 750 - 1500 ml. of Gatorade or a similar electrolyte-containing fluid during the session depending on their size, level of activity and body temperature.

Hyponatremia:

Participants will be given electrolyte solutions such as Gatorade instead of water in order to decrease the likelihood of dilutional hyponatremia. They will not be allowed to drink more than 3 L. of fluids over the course of the experimental session, and fluid intake will be spread out appropriately during the session. If there are any signs or symptoms of hyponatremia such as confusion, vomiting, myoclonus or ataxia, a stat serum sodium will be drawn and fluids will be withheld until the results are obtained. If the serum sodium is less than 125mEq/L, serum and urine osmolality and sodium will be measured, If serum sodium is less than 125mEq/L, serum and urine osmolality and sodium will be measured, and the subject will be transported to the ICU.

If a participant had low serum sodium during the experimental session and exhibited signs of clinically significant hyponatremia, then the principal investigator will not enroll the participant in any subsequent experimental sessions unless, in the clinical judgment of the investigators, further fluid restriction during the second experimental session would be a sufficient means of preventing hyponatremia.

Liver toxicity:

Liver enzymes will be measured as part of the initial screening visit. Volunteers with pre-existing abnormalities will be excluded from the study. If a participant exhibits signs of liver toxicity after an experimental session, then he or she will not receive a subsequent experimental session.

Neuropsychological toxicity:

Psychological and neurological status will be clinically monitored by the therapists during MDMA sessions and during therapy sessions at frequent intervals thereafter. If, on clinical examination after each experimental session, a participant is found to have cognitive deficits that persist for more than two weeks, this participant will not be given a subsequent experimental session.

Abuse and dependence:

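### A dosed participant who stops early has no planned T1 and/or T2 CAPS, so the ITT analysis may in effect compare completers (minor)

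*Protocol*

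**What the plan says.** **Replacement.** Under Protocol 2.7, "Participants enrolled in the study who withdraw during treatment or who the researchers decide for any reason should not continue in the study" count as drop-outs and will be replaced.

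**Visit dates.** Protocol 2.8.2 sets T1 three weeks after session 2, T2 three weeks after session 3, and T3 to T5 at 2, 6 and 12 months after session 3. Protocol 2.5 has the sessions "scheduled to occur three to five weeks apart". Protocol 2.8.1 gives a spacing of two to four weeks.

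**Rules that stop dosing (Protocol 2.8.8).**
- Sustained high blood pressure or heart rate "during an experimental session will not be given a subsequent experimental session".
- "Any participant who develops mania or psychosis will not be given a further MDMA session".
- After signs of liver toxicity, "then he or she will not receive a subsequent experimental session".
- Hyperthermia that does not settle quickly and persisting cognitive deficits have similar rules.
- Hospitalisation after severe panic suspends participation. If it follows the first session, "the investigator may elect to forego the further experimental sessions and drop the participant from the study", after discussion with the ethics committee.

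None of these rules says whether CAPS continues.

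**Analysis.** SAP 6.1 defines ITT as everyone randomised who had at least one experimental session, with all available data used. SAP 6.4.1 specifies a repeated-measures ANOVA of CAPS at baseline, T1 and T2, with condition as the between-groups factor. It names no method for missing scores. Separately, Protocol 2.8.3 plans to look at CAPS and PDS at baseline and "two months after each participant has undergone a final session, defined as the last experimental or open-label MDMA-assisted psychotherapy session".

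**The concern.** Question 2 of the protocol is the randomised comparison of full dose with low dose on CAPS. It keeps the protection of randomisation only if everyone randomised and dosed contributes an outcome. Here a person who stops dosing is formally in the ITT set, but the two follow-up scores that the main analysis needs are tied to sessions that he or she may never have.

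Unequal stopping is plausible on the protocol's own account. Protocol 4.2 expects minimal effects on vital signs at the low dose and significant rises in blood pressure and heart rate at the full dose. A stop for blood pressure alone need not be related to CAPS response. Withdrawal, a severe psychological reaction or an open-ended researcher decision could be.

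If poor responders were lost mainly from the full-dose arm, the comparison would lean towards MDMA. If they were lost mainly from the low-dose arm, it would lean the other way.

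**Working it through.** **1. Which CAPS visits have a date?**

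| Last session received | T1 | T2 | T3 to T5 |
|---|---|---|---|
| Session 1 | none | none | none |
| Session 2 | dated | none | none |
| Session 3 | dated | dated | dated |

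At a spacing of three to five weeks, T1 falls on or before the date planned for session 3. At the two-week minimum in Protocol 2.8.1 it would fall after that date.

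**2. Does another rule supply the missing CAPS?**
- Protocol 2.7.1 items 6 and 7 keep the 6- and 12-month visits despite added medication or therapy, but those visits are counted from session 3.
- Item 13 requires telephone contact when the schedule slips, not CAPS.
- Item 5 asks for willingness to complete follow-up and instruments, but sets no visit.
- Table 2 has no early-termination visit.
- The sentence in Protocol 2.8.3 comes closest. It adds no visit to 2.8.2, and its time point is not in SAP 6.4.1.
- PDS is taken the day after each session, but it is a self-report secondary measure and cannot stand in for CAPS.

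**3. What happens in the analysis?** A repeated-measures ANOVA that needs complete rows drops anyone without T1 or T2, together with the scores that person does have. That it needs complete rows is an assumption, because the SAP does not say.

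**4. Size if stopping is related to response.** The documents give no stopping rate, effect size or SD, so there is no figure to reproduce and everything below is illustrative.

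Model: no true effect; each dosed participant in the affected arm stops with probability p; stopping has correlation r with a worse CAPS change; each is replaced until the arms are 8 and 4.

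Shift in the completers' mean = r × φ(z) / (1 − p), where z is the normal quantile at 1 − p.

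| p | Chance of at least one stop among 8, 1 − (1 − p)^8 | Shift, r = 0.3 | Shift, r = 0.5 |
|---|---|---|---|
| 0.05 | 0.34 | 0.033 SD | 0.054 SD |
| 0.10 | 0.57 | 0.058 SD | 0.097 SD |
| 0.20 | 0.83 | 0.105 SD | 0.175 SD |

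The standard error for 8 v 4 is √(1/8 + 1/4) = 0.612 SD, so the shift is 0.033/0.612 = 5% to 0.175/0.612 = 29% of it. At an assumed change SD of 20 to 25 points, it is 0.033 × 20 = 0.7 to 0.175 × 25 = 4.4 CAPS points.

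**5. Effect on test error.** 100,000 simulated trials per setting, with correlation 0.5 between visits and unit SD assumed. Only the full-dose arm stops, over the grid above:

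| Test | No stopping | With stopping |
|---|---|---|
| SAP ANOVA, condition main effect | 4.95% | 4.90% to 5.05% |
| SAP ANOVA, condition by time | 5.02% | 5.05% to 5.75% |
| Protocol F1_LD_F1 interaction | 7.30% | 7.52% to 7.96% |
| t-test on T2 minus baseline, two-sided | 4.93% | 5.13% to 6.13% |
| Same t-test, tail favouring MDMA | 2.39% | 2.89% to 4.69% |

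If only the low-dose arm stops, the shifts reverse and the tail favouring MDMA falls to between 2.20% and 1.21%. With equal stopping in both arms (p = 0.10 or 0.20, r = 0.5), the shift is 0.003 or −0.001 SD and the two-sided error is 4.93% or 5.04%.

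**6. A simpler illustration.** Suppose the 8 full-dose completers fall by 15 to 30 CAPS points and one replaced drop-out does not change. The mean over all nine is 8/9 of the completers' mean, so the completers overstate that arm's fall by 15/9 = 1.7 to 30/9 = 3.3 points.

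**The case against.** The strongest reply is that no analysis set removes a replaced participant. SAP 6.1 keeps everyone dosed, so replacements join the ITT set and do not substitute for anyone. That stands. A reader might infer that replacement itself turns the comparison into one of completers. The documents do not support this: any harm comes from CAPS that is not collected and from a method that may need complete rows.

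A reader might also infer that every safety stop ends participation and triggers replacement. The text does not say so. Most rules in Protocol 2.8.8 only withhold sessions, and hospitalisation after panic suspends participation, with dropping optional. Equally, no rule says that CAPS goes on for these participants.

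Protocol 2.8.3 shows an intention to have scores two months after the last session. It is fair to say that a stopped participant is not wholly without a plan. It does not provide T1 or T2, which carry the controlled comparison.

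The absence of a visit rule cannot be fully confirmed. The SAP's time and events table is an attachment that is not shown. The SAP also cites an Amendment 5 that ended the six-month visits and Stage 3, both still present in the supplied protocol. A later version may differ.

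Finally, SAP 4.0 gives twelve randomised and twelve completed. Read literally, nobody stopped. Under a replacement rule, though, twelve completers would result either way, and the SAP does not say that nobody was replaced.

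**Conclusion.** The gap is real on the supplied text, and its importance is minor. A dosed participant who stops early has no planned T1 and/or T2 CAPS, and the ITT ANOVA would probably leave that person out. This rests on the assumption that the ANOVA needs complete rows.

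Under no true effect, bias needs stopping that is both related to CAPS response and different between arms. On the assumed grid it is 0.03 to 0.18 SD in either direction. The main-effect test that SAP 6.4.1 names stays at about 5%, and condition by time reaches at most 5.8%.

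A reader might infer that the trial's result is biased towards MDMA. The documents do not support that: they record no stop, give no rate, and leave the direction open.

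**What to change.** 1. **Protocol 2.7 and 2.8.2.** State that anyone who has had at least one experimental session and stops dosing stays in follow-up unless consent is withdrawn. CAPS is obtained at T1, T2 and T3, dated from the scheduled dates of sessions 2 and 3, or, if none was set, from a date 3 to 5 weeks after the previous session. Any replacement is additional.
2. **SAP 6.4.1.** Analyse ITT CAPS with a method that accepts an incomplete series, for example a mixed model, so that available baseline and T1 scores are used. This is the weaker half of the remedy. It relies on the observed scores to account for the missing ones, and someone with baseline alone adds little.
3. **SAP.** Accompany this with disposition by arm: everyone randomised and dosed, sessions received, reason for stopping, whether replaced, and CAPS visits available. If nobody stopped, one sentence saying so settles the matter.

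The SAP describes conduct in the past tense, so for completed participants only items 2 and 3 can still change.

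**Cost.** Up to three CAPS visits per stopped participant, a few sentences and a table. The estimate may look less favourable: one stopped participant among nine on full dose who gains none, or half, of the benefit dilutes that arm's effect by 1/9 = 11% or 0.5/9 = 6%. Precision is not lost if the stopped participant's CAPS is obtained: √(1/9 + 1/4) = 0.601 SD, against 0.612 SD for 8 v 4.

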2.8. Methods

2.8.1. Drugs and Dosage

Upon enrollment in the study, the participant will be randomly assigned to the Low Dose or the Fully Active Dose condition. Condition assignment will be performed with a table of random numbers generated by the Institute for Statistics, University of Bern. All study investigators will remain blind to condition assignment. If there is an adverse event or other emergency requiring knowledge of participant's condition assignment, the blind may be broken for an individual participant.

Participants in the Low Dose condition are assigned to receive an initial dose of 25 mg MDMA followed 2.5 hours later by a supplemental dose of 12.5 mg MDMA. Participants assigned to the Fully Active dose condition will receive an initial dose of 125 mg followed 2.5 hours later by a supplemental dose of 62.5 mg MDMA. Eight of 12 subjects, or 66.6%, will be assigned to the Fully Active dose condition, and 4 of 12, or 33.3%, will be assigned to the Low Dose condition.

The two doses of MDMA chosen for the Low Dose condition have been selected on the basis of their ability to produce minimal but detectable subjective effects (Grob et al. unpublished; Harris et al. 2002) and thus serve as an active placebo. The cumulative dose of 37.5 mg MDMA is not expected to produce a significant reduction in anxiety or a significant increase in access to emotionally upsetting material, though this dose may produce slight alterations in consciousness, such as increased relaxation or tension (Harris et al. 2002). The initial 125 mg dose of MDMA selected for the Fully Active Dose condition was chosen on the basis of case reports of MDMA-assisted psychotherapy conducted in the US prior to scheduling (Greer and Tolbert 1986), as well as on data obtained from [name] MAPS-sponsored MDMA/PTSD pilot study currently underway in the United States. This dose is expected to reduce fear in response to emotionally upsetting thoughts, feelings or memories and to increase access to emotionally intense material, and is thus expected to be therapeutically active. Doses equal to or exceeding 125 mg have been employed in previous uncontrolled and controlled studies of MDMA (Cami et al. 2000; Grob et al. 1996; Grob et al. Unpublished; Harris et al. 2002; Lester et al. 2000; Mas et al. 1999; Styk 2007; Tancer et al. 2001; Tancer et al. 2003; Vollenweider et al. 1998).

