2.8.5.1. Details of MDMA-assisted Experimental Sessions

The protocols will be exactly the same for each experimental session. All treatment sessions will begin at 10:00 AM and will take place at the office of [name] in Biberist, Switzerland. There will be sufficient equipment for assessing blood pressure, pulse and body temperature, and for dealing with potential adverse events, such as hypertension. In case of a hypertensive crisis the next hospital with emergency room and ICU is 5 minutes away from the office (Bürgerspital Solothurn). Ambient temperature will be kept comfortably cool to decrease the likelihood of hyperthermia. Participants will have had nothing by mouth except alcohol-free liquids since 12 AM on the evening before each experimental session. They will be asked to arrive at 9:00 AM for collection of a urine specimen for drug screening and, for females, a pregnancy test. These results must be negative for the subject to continue in the study. At the beginning of the session, the therapists will discuss with the participant his or her intentions for the session, including intentions regarding working with psychological issues related to their PTSD. Participants will complete the SUD just prior to initial dose administration (25 mg for Low Dose participants and 125 mg for Fully Active Dose participants). After the session begins, participants will lie or recline in a comfortable position with eyes closed or wearing eyeshades if preferred. They will listen to a program of music designed to support their experience by initially aiding relaxation and later evoking and supporting deep emotions and the emergence of unconscious material (Bonny and Savary 1990; Grof 2000: pp.186-191; Grof 1980; Unkefer 1990). After the first hour, if the participant has not spoken spontaneously, the therapist-investigators will check in with him/her about the nature of the experience. For the rest of the experience, as appropriate, the therapist-investigators will support and encourage the participant in emotional processing and resolution of whatever psychological material is emerging. The therapist-investigators will also encourage periods of time in which the participant remains silent with eyes closed and with attention focused inward in order to allow for the further unfolding of their inner experience. Electrolyte containing fluids will be available ad lib throughout the session within the limits described under "Monitoring for Toxicity." Food will be available during the latter part of the session.

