6.0 Analyses

6.1 Study population

See protocol. All participants were diagnosed with chronic PTSD, met DSM IV criteria, and had Global CAPS scores of 50 or greater upon enrollment. They had either undergone psychotherapy, pharmacotherapy or both without a significant reduction in PTSD symptoms.

All clinical data will be presented in tabular listings. All analyses will be carried out with SPSS of Version 12.0 or higher.

Definitions of subject populations for analysis:

All Enrolled: All participants who signed an informed consent form and completed baseline measures.

Intention to treat: All participants who were randomized to a condition and underwent at least one experimental session. All available data will be used.

Per Protocol: All participants who completed Stage 1 and underwent assessment of PTSD symptoms two months after the second experimental session. Analyses may be conducted with and without a participant who corresponds to a major protocol deviation.

Partial crossover: All participants who completed Stage 2 as well as Stage 1.

Extended Assessment 1: All participants who underwent assessment two, six and twelve months after their third Stage 1 or Stage 2 experimental session.

Extended Assessment 2: All participants who underwent Stage 3

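### Replacing randomised drop-outs, with CAPS visits timed only from sessions 2 and 3, can bias the Stage 1 comparison, in a direction that depends on who is lost

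*Protocol*

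**What the plan says.** Protocol 2.8.1 places randomisation before treatment: "Upon enrollment in the study, the participant will be randomly assigned to the Low Dose or the Fully Active Dose condition". The allocation is 2:1: "Eight of 12 subjects, or 66.6%, will be assigned to the Fully Active dose condition", and the other four go to the low dose.

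Protocol 2.7 says that drop-outs are replaced. It defines them as enrolled participants "who withdraw during treatment or who the researchers decide for any reason should not continue in the study". It does not say how a replacement is allocated, or whether the person replaced stays in the analysis.

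Protocol 2.8.2 ties the CAPS visits to sessions. T1 falls three weeks after session 2, and T2 is "3 weeks after the third experimental session (MDMA 3"). The later follow-ups also count from session 3. The SAP main analysis (6.4.1) uses baseline, T1 and T2 only. Neither document has a CAPS visit for someone who stops early, or a rule for missing scores.

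SAP 6.1 defines Intention to Treat as "All participants who were randomized to a condition and underwent at least one experimental session. All available data will be used". Per Protocol is limited to people who completed Stage 1.

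Protocol 2.8.8 lists reactions that end further sessions: sustained high blood pressure or heart rate, a temperature rise that does not settle, liver signs, lasting cognitive deficits, and mania or psychosis. After hospitalisation for a severe panic reaction at the first session, "the investigator may elect to forego the further experimental sessions and drop the participant from the study". Protocol 2.8.5.1 adds a drug screen and pregnancy test before each session: "These results must be negative for the subject to continue in the study".

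**The concern.** Randomisation protects the comparison only if the people compared are the people randomised. Here a participant can be taken out after dosing has begun and another put in. The one who leaves has no scheduled primary outcome at the end of treatment. The T2 comparison then becomes completers against completers.

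The loss need not be balanced. Protocol 4.2 expects clear rises in blood pressure and heart rate at full dose and minimal effects at 25 mg, so the physiological rules should bite mostly in one arm. With eight and four participants, one person is 12.5% or 25% of an arm.

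If losses are related to CAPS outcome and differ between arms, the estimated effect and its p-value are shifted by an amount the reader cannot recover unless randomised, stopped and replaced participants are counted by arm.

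**Working it through.** **The plan's own figures.** 8/12 = 66.7% and 4/12 = 33.3%, which agrees with Protocol 2.8.1 apart from rounding. The total of 12 cannot be reproduced, because no effect size, SD, power or drop-out rate is given. The plan states "Statistical significance will be set at 0.05" without saying one- or two-sided; two-sided is assumed below.

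**Which CAPS scores exist.**
- Stop after session 1: baseline only.
- Stop after session 2: baseline and T1 at most.
- Randomised, never dosed: baseline only, and outside the Intention to Treat set.

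A standard repeated-measures ANOVA on three time points drops all of these as incomplete cases.

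**Illustration in CAPS points.** Assumptions, none from the documents: eight full-dose completers gain G = 30 points on average; k full-dose participants stop and are replaced in the same arm; those who stop keep a fraction f of the gain.

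Mean over all randomised = G(8 + fk)/(8 + k). Overstatement = G(1 − f)k/(8 + k).

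| k | f = 0 | f = 0.5 | f = 1 |
|---|---|---|---|
| 1 | 240/9 = 26.7; over by 3.3 | 255/9 = 28.3; over by 1.7 | 30; 0 |
| 2 | 240/10 = 24.0; over by 6.0 | 270/10 = 27.0; over by 3.0 | 30; 0 |
| 3 | 240/11 = 21.8; over by 8.2 | 285/11 = 25.9; over by 4.1 | 30; 0 |

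The result scales with G: at k = 1 and f = 0 it is 20/9 = 2.2 points for G = 20 and 40/9 = 4.4 for G = 40. In the low-dose arm, one replaced participant with no gain makes the true mean 4/5 of the completers' mean. That error works against full dose.

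**Illustration with no true difference.** Let ρ be the correlation between the tendency to drop out and a poor outcome, and q = k/(8 + k) the fraction lost. Bias in SD units = ρ·φ(z_q)/(1 − q).
- Full-dose loss, ρ = 1: 0.21 (k = 1), 0.35 (k = 2), 0.46 (k = 3).
- Full-dose loss, ρ = 0.5: 0.11, 0.18, 0.23.
- Low-dose loss of one in five, ρ = 1: −0.35.
- Equally selective loss in both arms, or ρ = 0: zero.

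For scale, 8 against 4 has 80% power only for about 1.90 SD (t-test).

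In 40,000 simulated 8:4 trials with full-dose loss at q = 0.20, false positives favouring full dose were 9.6% at ρ = 1, 4.8% at ρ = 0.5 and 2.5% at ρ = 0, against 2.5% with no loss (t-test on change scores). An exact Mann-Whitney test gave 8.2%, 4.5% and 2.4%, against 2.3%. Both tests simplify the planned repeated-measures analysis.

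**The case against.** The strongest reply is that no direction of bias is shown. A blood pressure, temperature or liver stop is not a PTSD failure, and nothing in the documents links such stops to worse CAPS. That stands, and the calculation agrees: the sign depends on which arm loses people and whether loss follows outcome. A reader might infer that the plan favours full dose; the documents support that only as a conditional statement.

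A reader might also infer that every toxicity rule in 2.8.8 removes and replaces the participant. It does not. Most of those rules end sessions and are silent on study membership. The panic text does speak of leaving the study, but the removal is optional and follows discussion with the ethics committee. The urine tests are not shown to be dose-related. What remains is the open wording of 2.7, which lets any of these stops become a replacement.

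Some data survive early stopping. T1 can exist after session 2, and SAP 3.2 schedules the PDS on the day after each session. But the PDS is a secondary self-report measure and does not replace the CAPS.

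The investigators are meant to be blind (2.8.1). That limits deliberate selection, but not selection through reactions that themselves differ by dose. Omitting never-dosed participants cannot create bias from drug reactions, so that is the smaller defect.

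Finally, SAP 4.0 reports twelve assigned and twelve completing. If those are the same twelve, nothing was lost. A reader might equally infer that replacements took place. The documents settle neither, because they give no count of drop-outs or replacements.

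**Conclusion.** The concern holds in conditional form. Replacement after randomisation, together with CAPS visits that exist only relative to sessions 2 and 3, leaves the main comparison open to selection that the Intention to Treat set cannot repair. The bias is toward full dose if dose-related stops predict worse CAPS, against it if low-dose participants leave for lack of benefit, and absent if loss is equal or unrelated to outcome.

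Under the stated assumptions (30-point gain, one to three full-dose participants replaced), the overstatement runs from 0 to 8.2 points. The number replaced, the gain and the fraction kept are all assumed, so this is a range of possibilities and not an estimate for this trial. The plan should be changed. In a 12-person pilot that hypothesises only trends, the defect does not by itself invalidate the study.

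**What to change.** - **Protocol 2.7:** state that stopping sessions is not leaving the study. The existing independent assessor does CAPS T1 and T2, for all who agree, on calendar dates fixed from randomisation or first session. Inclusion criteria 6 and 7 already apply this principle to the 6- and 12-month visits, which go ahead whatever other treatment is taken.
- **Session interval:** the dates need one stated interval. Protocol 2.5 and 2.8.4 give three to five weeks between sessions and 2.8.1 gives two to four; these must be reconciled.
- **SAP 6.1:** define Intention to Treat as everyone randomised, in the assigned arm, including those never dosed. Replacements are additional randomised participants and do not displace the drop-out; state how they are allocated.
- **SAP 6.4.1:** use a method that keeps incomplete cases, and add a sensitivity analysis that counts drop-outs as no change.
- **Reporting:** give the numbers randomised, stopped and replaced by arm.

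The cost is a protocol paragraph, short SAP edits, and one or two CAPS interviews per stopped participant. If the visits are already past, the set definition, the sensitivity analysis and the by-arm counts can still be corrected. Clinical stopping rules are unchanged.
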